8 STUDY ASSESSMENTS AND PROCEDURES

Study procedures and their timing are summarized in the SoA ([Section 1.3](#)). Protocol waivers or exemptions are not allowed.

- Adherence to the study design requirements, including those specified in the SoA, is essential and required for study conduct.
- All screening evaluations must be completed and reviewed to confirm that potential participants meet all eligibility criteria. The Investigator will maintain a screening log to record details of all participants screened and to confirm eligibility or record reasons for screening failure, as applicable.
- Procedures conducted as part of the participant's routine clinical management (eg, blood count, urine tests) and obtained before signing of the ICF may be utilized for screening or baseline purposes provided the procedures met the protocol-specified criteria and were performed within the timeframe defined in the SoA.
- Safety/laboratory/analyte results that could unblind the study will not be reported to investigative sites or other blinded personnel until the study has been unblinded.
- In case a study procedure is not performed, or not performed in time due to COVID-19, it is important to capture this specific deviation related information in the eCRF and explain the basis of the missing or delayed data, including the relationship to COVID-19.
- The maximum amount of blood collected from each participant over the duration of the study, including any extra assessments that may be required, will be within a safe limit for human clinical trials as recommended by the local Institutional Review Boards (IRB) and Independent Ethics Committees (IEC).
- Repeat or unscheduled samples may be taken for safety reasons or for technical issues with the samples.

It is recommended that assessments/procedures at a site visit are performed in the following order if applicable and possible:

- PROs and other questionnaires
- ECG
- Procedures:
 - FeNO measurement
 - Impulse oscillometry
 - Spirometry
 - eDiary download
 - Safety and laboratory assessments
 - Administration of IMP

Remote spirometry (pre-BD) and PEF measurements to be performed by participants daily in the AM and PM.

For a regional or national emergency declared by a governmental agency, contingency measures are included in Appendix 9: Contingency measures for a regional or national emergency that is declared by a governmental agency ([Section 10.9](#)).

8.1 EFFICACY ASSESSMENTS

Planned timepoints for all assessments are provided in the SoA ([Section 1.3](#)).

8.1.1 Primary endpoint

The primary endpoint for this study is the annualized rate of severe exacerbation events over a period of 48 weeks.

8.1.1.1 Severe asthma exacerbation events

Severe asthma exacerbation event is defined as:

- Worsening of asthma requiring the use of systemic corticosteroids for ≥ 3 days or, in the case of a stable maintenance regimen of OCS for the treatment of asthma, a doubling of the dose for 3 or more days; or
- Hospitalization or emergency room visit because of asthma, requiring systemic corticosteroids.

8.1.2 Secondary endpoints

8.1.2.1 Key secondary endpoints

Key secondary endpoints include:

- Change from baseline in pre-BD FEV1 at week 48
- Change from baseline in ACQ-5 score at Week 48
- Change from baseline in AQLQ (S) Self-Administered Score at Week 48

8.1.2.2 Efficacy endpoints

Other secondary efficacy endpoints include:

- Change from baseline in post-BD FEV1 at week 48
- The absolute change in the percent predicted FEV1 from baseline to week 48 (pre-BD and post-BD)
- Change from baseline in ACQ-5 score at Weeks 2, 4, 8, 12, 24, 36, and 60

- Time to first severe exacerbation event
- Change from baseline in pre-BD and post-BD FEV1 and other lung function measurements (PEF, FVC, and FEF 25-75%) at each spirometry endpoint
- Change from baseline in FeNO at Weeks 2, 4, 8, 12, 16, 24, 36, 48, and 60
- Annualized rate of LOAC events, during 48 weeks of treatment, defined by one or several of the following criteria:
 - A 30% or greater reduction from baseline in morning PEF on 2 consecutive days.
 - ≥ 6 additional reliever puffs of SABA OR ≥ 4 additional puffs of low-dose ICS/formoterol in a 24-hour period (compared to baseline) on 2 consecutive days
 - Increase in ICS ≥ 4 times than the Visit 2 dose
 - Worsening of asthma requiring the use of systemic corticosteroids for ≥ 3 days or, in the case of a stable maintenance regimen of OCS for the treatment of asthma, a doubling of the dose for 3 or more days
 - Hospitalization or emergency room visit because of asthma, requiring systemic corticosteroids severe exacerbation event
- Time to first LOAC event
- Change from baseline in the ADSD 6-item daily morning score and in the ANSD 6-item daily evening scores at Weeks 2, 4, 8, 12, 24, 36, 48, and 60
- Annualized rate of severe asthma exacerbations requiring hospitalization or emergency room or urgent care visit during 48 weeks of treatment
- Change from baseline in the numbers of inhalations/day of SABA or low-dose ICS/formoterol for symptom relief at Weeks 2, 4, 8, 12, 24, 36, 48, and 60
- Change from baseline in AQLQ (S) Self-Administered Score at Weeks 2, 4, 8, 12, 24, 36, and 60
- Change from baseline in SGRQ at Weeks 2, 4, 8, 12, 24, 36, 48, and 60
- Proportion of participants with a decrease from baseline of at least 4 points in SGRQ total score at Week 48
- Change from baseline in ACQ-6 and ACQ-7 score at Weeks 2, 4, 8, 12, 24, 36, 48, and 60

8.1.3 Disease-specific efficacy measures

8.1.3.1 Spirometry

Spirometry will be performed in accordance with the ATS/ERS guidelines (34) and prior to administration of IMP at the planned time point (Section 1.3, SoA). For pre-BD measured parameters, including FEV1, PEF, FVC and FEF 25%-75%, spirometry will be performed after a wash out period of bronchodilators according to their action duration, following the guidance of the ATS/ERS 2019 guidance (34). For example, withholding the last dose of salbutamol/albuterol or levosalbutamol/levalbuterol for at least 6 hours, withholding the last dose of LABA for at least

24 hours, and finally the last dose of ultralong-acting LABA (like vilanterol) or the last dose of LAMA should be withheld for at least 36 hours). This will be verified before performing the measurements. In addition, participants are asked to avoid consuming alcohol 8 hours prior to spirometry, and to avoid engaging in strenuous exertion for at least 30 minutes prior to all lung function assessments.

At all site visits, spirometry will be performed preferably in the morning, afternoon is allowable in the exceptional circumstance when morning spirometry cannot be performed. Spirometry will be done at approximately the same time at each visit throughout the study. The same spirometer and standard spirometric techniques, including calibration, will be used to perform spirometry at all visits, and whenever possible, the same person should perform the measurements. Three measurements fulfilling the ATS acceptability and repeatability criteria should be obtained at every site visit, if possible.

Reversibility is defined as an increase of the absolute FEV1 after administration of bronchodilator and is measured by spirometry as post-BD increase in FEV1 in percent of the pre-BD FEV1. After spirometry for measuring pre-BD FEV1, participants will receive 2-4 puffs of albuterol/salbutamol or levalbuterol/levosalbutamol from a primed MDI. Reversibility may be performed using inhalation of nebulized albuterol/salbutamol or levalbuterol/levosalbutamol, if it is consistent with usual office practice (to be documented). The post-BD spirometry may be repeated several times within 30 minutes after administration of bronchodilator.

Further details on spirometry will be available in a separate operational manual provided to the sites.

8.1.3.2 Asthma Control Questionnaire, versions 5, 6, and 7

The ACQ is a questionnaire that measures the adequacy of asthma control and any changes in asthma control that may occur spontaneously or as a result of treatment. The ACQ-5 has five questions on the asthma symptoms and patients are asked to recall how their asthma has been during the previous week. The ACQ-6 includes an additional item that scores the average number of daily puffs needed from a SABA bronchodilator during the past week and the ACQ-7 includes this SABA item, plus a final clinic-assessed item scoring FEV1% predicted. Each item of the ACQ is measured on a 7-point response scale (0=no impairment, 6=maximum impairment). The ACQ score is the mean of the item responses and ranges from 0 (totally controlled) and 6 (severely uncontrolled). A high score indicates low asthma control. Participants with a score below 1.0 reflect adequately controlled asthma and participants with scores above 1.0 reflect inadequately controlled asthma (35). On the 7-point scale of the ACQ questionnaires, a change or difference in score of 0.5 is the smallest change that can be considered clinically important, corresponding to the Minimal Clinically Important Difference (MCID) defined by the developer (36).

Measurement properties such as reliability and ability to detect change have been documented in the literature (36). Participants will complete the questionnaires in an eDiary during on-site visits as described in the SoA (Section 1.3).

8.1.3.3 Fractional Exhaled Nitric Oxide

Fractional Exhaled Nitric Oxide (FeNO) is a measure of nitric oxide in exhaled breath produced by epithelial cells in the lung and considered as a biomarker of Type-2 inflammation in asthma. FeNO levels (ppb) will be collected on site with a dedicated medical device (such as a commercially available hand worn device NIOX VERO®)). The FeNO test needs to be completed prior to impulse oscillometry and spirometry in order to avoid any impact on the nitric oxide measurement. In addition, participants should not eat or drink 1 hour prior to having the FeNO test, as this may affect the results. Further details on the procedure for measuring exhaled nitric oxide with NIOX VERO will be provided in a separate instruction manual.

8.1.3.4 Electronic diary

Electronic diary (eDiary) is a handheld device used for daily recording of reliever use, asthma controller drug use, ADSD and ANSD, and recording of participant's answers to the ACQ-6, AQLQ(S), and other PROs questionnaires during the scheduled visits. This handheld device is dispensed at Visit 1 with including instructions for use and recorded information is downloaded from this device on the other indicated days. For each site visit, the participants will bring their electronic devices and will complete the questionnaire on site. Electronic handheld devices will be returned to the vendor at EOS at the latest.

On a daily basis throughout the study, the participant uses an eDiary to:

- Respond to the morning and evening asthma symptom score ADSD/ANSO questions.
- Indicate the number of inhalations/day of reliever medications for symptom relief.
- Record the use of controller medications per day.

8.1.3.5 Loss of asthma control events

Annualized rate of LOAC events, during 48 weeks of treatment, defined by one or several of the following criteria:

- A 30% or greater reduction from baseline in morning PEF on 2 consecutive days.
- ≥ 6 additional reliever puffs of SABA OR ≥ 4 additional puffs of low-dose ICS/formoterol in a 24-hour period (compared to baseline) on 2 consecutive days
- Increase in ICS ≥ 4 times than the Visit 2 dose
- Worsening of asthma requiring the use of systemic corticosteroids for ≥ 3 days or, in the case of a stable maintenance regimen of OCS for the treatment of asthma, a doubling of the dose for 3 or more days
- Hospitalization or emergency room visit because of asthma, requiring systemic corticosteroids severe exacerbation event

Participants will measure their PEF using electronic spirometer (e-Spirometer) ([Section 8.1.3.9](#)). Reliever medication use will be recorded in the eDiary ([Section 8.1.3.4](#)).

8.1.3.6 Asthma Daytime Symptom Diary and Asthma Nighttime Symptom Diary

The ADSD and ANSD are PRO measures developed by the PRO Consortium' Asthma Working Group. Both instruments have been designed to measure asthma symptoms in adult and adolescent (12 years of age and older) patients diagnosed with mild-to-severe asthma. ADSD and ANSD assess asthma severity based on patient self-report of asthma core symptoms, ie, difficulty of breathing; wheezing; shortness of breath; chest tightness; chest pain; and cough. Patients are asked to complete the ADSD every night before they go to bed, thinking about their asthma symptoms today, from when they got up this morning until now; the ANSD when getting up, thinking about their asthma symptoms last night from when they went to bed until now. They have demonstrated adequate evidence of content validity and cross-sectional measurement properties (ie, internal consistency reliability, test-retest reliability, convergent validity, and known-groups validity) to measure symptoms of asthma. Average scores are calculated for both the morning and evening diaries, referred to as the "6-Item ADSD Daily Morning Score" and "6-Item ANSD Daily Evening Score", respectively, using 6 out of 6 of the ADSD items (note: no weighting so each item contributes equally).

Both the ADSD and ANSD are composed of 6 items rated using an 11-point NRS that ranges from 0=None to 10=As bad as you can imagine (37). The participants will record their daytime and nighttime asthma symptoms in an eDiary, once in the evening and once in the morning, respectively. The participants will complete the ADSD and the ANSD as per SoA (Section 1.3).

8.1.3.7 Asthma Quality of Life Questionnaire with Standardized Activities Self-administered Score

The AQLQ(S) was designed as a self-administered participant reported outcome to measure the functional impairments that are most troublesome to adolescents and adults ≥ 12 years of age as a result of their asthma over the past two weeks. The instrument is comprised of 32 items, each rated on a 7-point Likert scales from 1 to 7. The AQLQ(S) has 4 domains. The domains and the number of items in each domain are as follows:

- Symptoms (11 items)
- Activity limitation (12 items, 5 of which are individualized)
- Emotional function (5 items)
- Environmental Exposure (4 items)

A global score is calculated ranging from 1 to 7 and a score by domain. Higher scores indicate better quality of life. The instrument has been used in many clinical trials, and it has been shown to be reliable, valid (patient interviews), and sensitive to change. The MCID for AQLQ(S) is 0.5 (38). Participants will complete the questionnaire in an eDiary during on-site visits as described in the SoA.

8.1.3.8 St. George's Respiratory Questionnaire

The SGRQ is a 50-item questionnaire designed to measure and quantify health status in adult patients with chronic airflow limitation (39, 40). A global score ranges from 0 to 100. Scores by

dimension are calculated for three domains: Symptoms (8 items), Activity (16 items) and Impacts (26 items) as well as a total score. Lower score indicates better quality of life (QoL). The first part ("Symptoms") evaluates symptomatology, including frequency and severity of cough, sputum production, wheeze, breathlessness and the duration and frequency of attacks of breathlessness or wheeze. The second part has two components: "Activity" and "Impacts". The "Activity" section addresses disturbances to patients' daily physical activities. The "Impacts" section covers a range of effects that chest troubles may have on patients' daily life and psycho-social functions (eg, daily life activities and functioning, employment, physical functioning, emotional impact, stigmatization, and patients' perceptions when treated). The MCID is 4 points for SGRQ (41). The recall period of the questionnaire is over the past 4 weeks.

The following efficacy parameters will be analyzed by assessing exploratory endpoints:

8.1.3.9 Remote spirometry

On a daily basis throughout the study, the participant uses an e-spirometer to measure morning and evening FEV1, and PEF. E-spirometer will be dispensed at screening (Visit 1). Initial training and written instructions will be provided for participants during screening with additional reminder training/instructions at regular intervals throughout the study.

The following instructions will be provided to the participant and are described in the study manual:

- Participants will be instructed to perform expiratory flow maneuvers
- AM e-spirometry is to be performed within 15 minutes after arising (between 5:30 AM and 12:00 PM) prior to taking any reliever medication (SABA or low-dose ICS/formoterol).
- PM e-spirometry is to be performed in the evening (between 5:30 PM and 12 AM) prior to taking any reliever medication (SABA or low-dose ICS/formoterol).
- Participants should try to withhold reliever medication (SABA or low-dose ICS/formoterol) for at least 6 hours prior to e-spirometry.
- Three e-spirometry efforts will be performed by the participant; all 3 values will be recorded by the e-spirometer, and the highest value will be used for evaluation.

Baseline AM e-spirometry data (FEV1 and PEF) will be the mean AM measurement recorded for the 7 days prior to the first dose of investigational product, and baseline PM data will be the mean PM measurement recorded for the 7 days prior to the first dose of investigational product. Period stability limit is defined as the respective mean AM or PM data obtained over the last 7 days prior to Day 1. There should be at least 4 days' measurement for setting up the stability limit, and the first dosing visit should be rescheduled until data for 4 days are available.

8.1.3.10

[REDACTED]

[REDACTED]

[REDACTED]

[REDACTED]

[REDACTED]

[REDACTED]

[REDACTED]

[REDACTED]

[REDACTED]

[REDACTED]

[REDACTED]

[REDACTED]

[REDACTED]

8.1.3.11 [REDACTED]

[REDACTED]

[REDACTED]

[REDACTED]

[REDACTED]

[REDACTED]

[REDACTED]

[REDACTED]

[REDACTED]

[REDACTED]

[REDACTED]

[REDACTED]

[REDACTED]

[REDACTED]

[REDACTED]

[REDACTED]

[REDACTED]

[REDACTED]

[REDACTED]

[REDACTED]

[REDACTED]

[REDACTED]

[REDACTED]

[REDACTED]

[REDACTED]

[REDACTED]

[REDACTED]

[REDACTED]

[REDACTED]

[REDACTED]

[REDACTED]

[REDACTED]

[REDACTED]

[REDACTED]

[REDACTED]

[REDACTED]

8.1.3.12 Digital inhaler to measure the use of bronchodilator therapy

Digital inhalers will be optional and will be available in certain countries to measure the reliever medication use (bronchodilator therapy, inhalations/day). Further details will be available in a separate operational manual.

8.1.3.13 [REDACTED]

[REDACTED]

8.1.3.14 [REDACTED]

[REDACTED]

8.1.3.15 [REDACTED]

[REDACTED]

[REDACTED]

[REDACTED]

[REDACTED]

8.2 SAFETY ASSESSMENTS

This section presents safety assessments other than AEs which are presented in [Section 8.3](#).

Planned timepoints for all safety assessments are provided in the SoA ([Section 1.3](#)).

8.2.1 Physical examinations

- A complete physical examination will include skin, nasal cavities, eyes, ears, respiratory, cardiovascular, gastrointestinal, neurological, lymphatic, and musculoskeletal systems. Height and weight will also be measured and recorded at Screening (the participant is allowed to wear indoor, daytime clothing with no shoes). Weight will also be measured and recorded at the Baseline/Randomization (Visit 2), Week 24 (Visit 9), Week 48 (Visit 11), EOT (Visit 12) and EOS (Visit 13) or early discontinuation.
- Investigators should pay special attention to clinical signs related to previous serious illnesses and pay special attention to signs or symptoms of infection or malignancy.
- Any new finding or worsening of previous finding should be reported as a new AE.

Local Skin Reactions

On IMP administration days, local skin reactions around the site of injection will be assessed by the Investigator or other appropriately trained site personnel 30 minutes after the injection. Light pressure will be applied at the injection site and any pain, itchiness, tenderness, erythema, and induration will be recorded in the eCRF. Pain and tenderness will be assessed according to the following scale:

- Definitions of pain and tenderness:
 - None nothing
 - Mild easily tolerated
 - Moderate interferes with daily activities
 - Severe prevents normal everyday activities or sleep

Erythema and induration will be measured using a ruler, or a template supplied by the Sponsor.

8.2.2 Vital signs

- Oral/Tympanic/Rectal/Axillary/Skin/Temporal artery temperature, pulse rate, respiratory rate, and blood pressure will be assessed.
- Blood pressure and pulse measurements will be assessed with a completely automated device. Manual techniques will be used only if an automated device is not available.
- Blood pressure and pulse measurements should be preceded by at least 5 minutes of rest for the participant in a quiet setting without distractions (eg, television, cell phones).

8.2.3 Electrocardiograms

- Single 12-lead electrocardiogram (ECG(s)) will be obtained as outlined in the SoA (see [Section 1.3](#)) using an ECG machine that automatically calculates the heart rate and measures PR, QRS, QT, and corrected QT (QTc) intervals. The ECGs will be obtained prior to laboratory assessments and prior to spirometry. A qualified Investigator or appropriate designee (qualified physician) should review the ECGs in a timely manner to determine if there are any safety concerns and for clinical management of the participant. In case of abnormal findings identified by the qualified Investigator or appropriate designee (qualified physician), the ECG should be provided to the cardiologist for further confirmation and description of findings. The Investigator must always date and sign the ECG and comment on the assessment before filing this in the medical records. In the event of any clinically significant abnormal finding that meet the definition of an AE ([Section 10.3](#)), the Investigator will continue to monitor the participant with additional ECGs until the ECG findings return to baseline ECG findings or the Investigator determines that follow-up is no longer necessary.
- Any clinically significant ECG related to a preexisting condition at Screening (Visit 1) that does not affect the conduct of the study per the Investigator's judgment will need to be well documented in the source documentation.

8.2.4 Clinical safety laboratory tests

- See Appendix 2 ([Section 10.2](#)) for the list of clinical laboratory tests to be performed and to the SoA ([Section 1.3](#)) for the timing and frequency.
- The Investigator must review the laboratory report, document this review, and record any clinically significant changes occurring during the study as an AE. The laboratory reports must be filed with the source documents. Abnormal laboratory findings associated with the underlying disease are not considered clinically significant, unless judged by the Investigator to be more severe than expected for the participant's condition.
- All laboratory tests with values considered clinically significantly abnormal during participation in the study should be repeated until the values return to normal or baseline or are no longer considered clinically significant by the Investigator.
 - If such values do not return to normal/baseline within a period of time judged reasonable by the Investigator, the etiology should be identified and the Sponsor notified.

- All protocol-required laboratory tests, as defined in Appendix 2 ([Section 10.2](#)), must be conducted in accordance with the laboratory manual and the SoA ([Section 1.3.](#))
- If laboratory values from non-protocol specified laboratory tests performed at the institution's local laboratory require a change in participant management or are considered clinically significant by the Investigator (eg, SAE or AE or dose modification), then the results must be recorded.
- Critical values alerts are linked to extremely high or low laboratory test values which are considered to be potentially life threatening. In the event a critical value is reported, Central Laboratory will contact the site.
- Special procedures for collection, storage, and shipping of serum are described in the Central Laboratory Manual.
- At Screening, hepatitis serology testing is performed in order to rule out active or chronic infection. Guidance on hepatitis serology eligibility interpretation is provided in [Table 7](#).

Table 7 - Hepatitis serology testing

Hepatitis serology result	Protocol action
HBs Ag: positive or indeterminate	Excluded
HBs Ab positive, HBsAg negative, HBc Ab: negative	Eligible
HBc Ab IgM: positive	Excluded
HBc Ab Total: positive (with or without HBs Ab positive)	Test for HBV DNA If HBV DNA Positive: Excluded If HBV DNA Indeterminate: Eligible
HCV antibody: positive	Test for HCV RNA If HCV RNA Positive: Excluded If HCV RNA Indeterminate: Eligible

DNA = deoxyribonucleic acid; HBc Ab = total hepatitis B core antibody; HBc Ab IgM = IgM antibody to hepatitis B core antigen; HBsAg = hepatitis B surface antigen; HBV = hepatitis B virus; HBs Ab = hepatitis B surface antibody; HCV = hepatitis C virus; Ig = immunoglobulin.

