- f Clinical laboratory testing at Screening (Visit 1) will include a hepatitis screen covering hepatitis B surface antigen (HBs Ag), hepatitis B surface antibody (HBs Ab), total hepatitis B core antibody (HBc Ab), IgM antibody to hepatitis B core antigen (IgM HBc Ab), hepatitis C virus antibodies (HCV Ab), HIV screen (anti-HIV-1 and HIV-2 antibodies). In case of results showing HBs Ag (negative), and HBc Ab Total (positive), HBV DNA testing will be performed prior to randomization to rule out a false positivity to clarify the serological status. In case of results showing HCV Ab (positive), HCV RNA testing will be performed to rule out a false positivity. Please refer to Table 7 in Section 8.2.4.
- g Hematology: hemoglobin, hematocrit, platelet count, total white blood cell (WBC) count with five-part differential count, and total red blood cell count. Serum chemistry: creatinine, blood urea nitrogen, glucose, uric acid, total cholesterol, total protein, albumin, total bilirubin (in case of values above the normal range, differentiation in conjugated and non-conjugated bilirubin), alanine aminotransferase, aspartate aminotransferase, alkaline phosphatase, lactate dehydrogenase, electrolytes (sodium, potassium, chloride), bicarbonate, and creatine phosphokinase. The blood sample for serum chemistry must be taken with the participant in fasting state which means no intake of any food or drink except for water for at least 8 hours (if the visit can only be done at a different time of the day and the participant is not fasting, then he/she should be advised to eat light food and the site should document that serum chemistry was not obtained under fasting conditions). Urinalysis will include specific gravity, pH, glucose, ketones, blood, protein, nitrite, leukocyte esterase, urobilinogen, and bilirubin. If any urinalysis parameter on the dipstick is abnormal, a urine sample should be sent to the central laboratory for quantitative measurement. If urinalysis sample is abnormal for protein and/or red blood cells, microscopic analysis will be performed by the central laboratory.
- h The ECGs will be obtained prior to laboratory assessments and prior to spirometry.

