Note: TB testing is mandatory to rule out active/latent TB and should be performed, assessed and documented according to local guidelines. If no local guidelines are available or are not able to be performed at the site, a blood sample for Quantiferon testing should be sent to the central laboratory. Participants with confirmed positive TB test are excluded from the study unless all of the following conditions are met:

- a) have a history of prior documented completed chemoprophylaxis for latent TB infection (with a treatment regimen as per local guidelines), OR treated for active TB infection,

AND

- b) have obtained consultation with a specialist to rule out or treat active TB infection,

AND

- c) for whom review and approval from Sponsor have been granted are eligible.

- E 11. A history of malignancy of any type (excluding basal and squamous cell skin cancer and in situ cervical carcinoma that has been excised and cured >3 years prior to baseline).

- E 12. History of solid organ transplant.
- E 13. Participants positive for human immunodeficiency virus; participants with any of the following result at Screening (Visit 1): Positive (or indeterminate) hepatitis B surface antigen (HBs Ag) or positive IgM antibody to hepatitis B core antigen (IgM HBc Ab) or positive total hepatitis B core antibody (HBc Ab) confirmed by positive hepatitis B virus (HBV) DNA or positive hepatitis C virus total antibody (HCV Ab) confirmed by positive hepatitis C virus (HCV) RNA. Guidance on hepatitis serology eligibility interpretation is provided in [Table 7](#) in [Section 8.2.4](#).

Note for Japan: For Japan, the presence of HBsAg with/without positive HBV-DNA test result or the presence of HBc Ab or the presence of HBs Ab with positive HBV-DNA test result at screening or within 3 months prior to the screening visit is an exclusion criterion.

- E 14. Clinically significant laboratory abnormalities at Screening (Visit 1):
- Alanine aminotransferase (ALT) or aspartate aminotransferase (AST) >2 times upper limit of normal range (ULN).
 - Serum total bilirubin $>1.5 \times \text{ULN}$ (participants with Gilbert's syndrome can be included with total bilirubin $>1.5 \times \text{ULN}$ as long as direct bilirubin is $<1.5 \times \text{ULN}$).
 - Hemoglobin $<10 \text{ g/100 mL}$ for male and $<9 \text{ g/100 mL}$ for female.
 - Neutrophils $<1500/\mu\text{L}$ ($<1000/\mu\text{L}$ for those of African descent).
 - Platelets $<100\,000/\mu\text{L}$.

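### Table 7 makes HBc Ab-positive or HCV Ab-positive participants eligible when the confirmatory HBV DNA or HCV RNA result is indeterminate, and nothing requires that result to be resolved before randomization

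*Protocol*

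**What the plan says.** Protocol Section 8.2.4 states that "hepatitis serology testing is performed in order to rule out active or chronic infection". Table 7 then gives the eligibility action for each serology result.

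- The row for "HBs Ag: positive or indeterminate" leads to exclusion. So does a positive HBc IgM.
- Positive total HBc Ab leads to an HBV DNA test, with the outcome "If HBV DNA Positive: Excluded If HBV DNA Indeterminate: Eligible".
- Positive HCV antibody leads to an HCV RNA test, with the outcome "If HCV RNA Positive: Excluded If HCV RNA Indeterminate: Eligible".

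E 13 in Section 5.2 also excludes an indeterminate HBs Ag. For the antibody-positive groups it excludes only on a positive confirmatory test. The HCV part reads "positive hepatitis C virus total antibody (HCV Ab) confirmed by positive hepatitis C virus (HCV) RNA", and the HBc Ab part is built the same way. E 13 then refers the reader to Table 7: "Guidance on hepatitis serology eligibility interpretation is provided in" that table.

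Footnote f of the Schedule of Activities covers participants with negative HBs Ag and positive total HBc Ab, and says that "HBV DNA testing will be performed prior to randomization to rule out a false positivity to clarify the serological status". It asks for HCV RNA after a positive HCV antibody, again to rule out a false positive, but gives no timing relative to randomization.

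**The concern.** The DNA or RNA test is there to settle what a positive antibody leaves open. An indeterminate result does not settle it, yet Table 7 lets the participant in. The same table treats an indeterminate HBs Ag as disqualifying, and Appendix 2 (Section 10.2) sets out what must happen after an indeterminate tuberculosis test. For the hepatitis confirmatory tests there is no such path.

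What is at stake is a screening safety gate. The risk table in Section 2.3.1 says that OX40L blockade might reduce control of infections, although the same entry says there is no evidence that serious infections would be exaggerated with this mechanism. A site that follows Table 7 literally could dose someone whose HBV or HCV status is unresolved.

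**Working it through.** No arithmetic bears on the point itself, so the check is textual.

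**Step 1. Table 7 against E 13.**

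| Screening result | Table 7 | E 13 |
|---|---|---|
| HBs Ag indeterminate | Excluded | Excluded |
| HBc IgM positive | Excluded | Excluded |
| HBc Ab total positive, HBV DNA positive | Excluded | Excluded |
| HBc Ab total positive, HBV DNA indeterminate | Eligible | Not excluded |
| HBc Ab total positive, HBV DNA negative | No entry | Not excluded |
| HCV Ab positive, HCV RNA positive | Excluded | Excluded |
| HCV Ab positive, HCV RNA indeterminate | Eligible | Not excluded |
| HCV Ab positive, HCV RNA negative | No entry | Not excluded |

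The two sources agree. Two of the five Table 7 rows are affected. The missing entry for a negative result is what makes a slip plausible.

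**Step 2. Does any other text force resolution before randomization?**

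- Footnote f requires the HBV DNA test to be done before randomization. It sets no rule for an indeterminate result.
- Section 5.4 allows repeats at the Investigator's discretion for tests that fail the criteria. Table 7 has already called these participants eligible, so that text is not triggered.
- Section 8 (repeat or unscheduled samples) and Appendix 2 (additional tests) are permissions.
- Section 8 also requires all screening evaluations to be completed and reviewed to confirm eligibility. Under Table 7, that review returns eligible.
- A bullet in Section 8.2.4 says that values judged clinically significantly abnormal during participation should be repeated. It depends on that judgement and does not name an indeterminate PCR.
- E 07 (active or chronic infection) and E 27 (Investigator judgement) allow a site to exclude such a participant but do not require resolution. E 14 catches only raised liver tests and other laboratory abnormalities.
- Appendix 6 calls for HCV RNA, and for HBV DNA if clinically indicated, only after an ALT rise on study.

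None of these requires it.

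**Step 3. Comparison with tuberculosis.** Appendix 2 allows a repeat after an indeterminate TB test. After two indeterminate results, randomization needs no signs of infection, no high TB risk, no origin in an endemic area, and specialist exclusion of active disease. So the protocol elsewhere recognises that an indeterminate result needs a path.

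**Step 4. Japan.** The Japan note to E 13 (Sections 5.2 and 10.8.1) can be read two ways. If the positive-DNA condition attaches only to HBs Ab, HBc Ab alone excludes and the HBV gap does not exist there. If it attaches to both antibodies, the gap remains. The note does not mention HCV.

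**Step 5. Reach.** The number affected is about 420 × P(HBc Ab or HCV Ab positive) × P(indeterminate DNA or RNA, given positive). The documents give neither probability, so no count can be derived, and it may be zero.

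**Step 6. Timing.** SAP Section 3.8 gives 22 April 2024 as the date by which all randomized participants had completed Week 24. Week 24 is Day 169, so the last Day 1 was about 22 April 2024 − 168 days = 6 November 2023 (3 to 9 November with an assumed ±3-day window). Enrolment was therefore closed before SAP version 2 (11 May 2024). The last-randomized participant still had doses due at Week 36 (6 November 2023 + 252 days = 15 July 2024) and Week 48 (+ 336 days = 7 October 2024).

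**The case against.** The strongest reply has four parts.

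**A deliberate difference for HBV.** Footnote f orders HBV DNA when HBs Ag is already negative, and a positive HBc IgM is excluded separately. An indeterminate HBs Ag leaves the first-line marker open, whereas an indeterminate DNA arises after that marker is negative. Treating the two differently could be a design choice. This has some force for HBV, but it is not stated as a rationale and does not reach the HCV row.

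**A slip for negative.** If so, the protocol is silent on indeterminate results and does not tell sites to enrol them. This stands as a possibility. A reader might infer that the defect is the same either way, but silence and an affirmative rule are different faults, and the documents do not show which was meant. Sites can only act on what is written, and on either reading the rows need correcting.

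**An unseen laboratory manual.** Section 8.2.4 requires tests to follow that manual, which may hold repeat rules for equivocal assays. That is possible, but E 13 names Table 7 as the eligibility guidance.

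**No demonstrated harm.** No affected participant is shown, and with enrolment closed a rewording alone protects nobody in this trial. Both statements are correct, and they set the severity.

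**Conclusion.** The point holds as a minor one. As written, Table 7 admits participants whose confirmatory HBV DNA or HCV RNA result is indeterminate, against the section's own stated purpose, and no available text requires the result to be resolved first. It affects two of five rows. The HBV part may not apply in Japan. The number of participants is unknown, probably very small and possibly zero. Endpoint, power and alpha are not affected.

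Three stronger readings are not supported:

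- A reader might infer that Table 7 contradicts E 13. It does not. The inconsistency lies in how an indeterminate result is treated for HBs Ag compared with DNA or RNA.
- A reader might infer that known infection is let through. Positive or indeterminate HBs Ag, positive HBc IgM and positive DNA or RNA all still exclude.
- A reader might take the number of participants with treatment remaining as the size of the problem. That counts everyone still being dosed, not those with a positive antibody and an indeterminate confirmatory result.

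The verdict assumes that the text of Table 7 is what sites used and that the laboratory manual does not override it.

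**What to change.** In both rows of Table 7, replace the action with three entries: negative or undetectable, eligible; positive, excluded; indeterminate, repeat before randomization and exclude unless resolved as negative. Align E 13 with this, and carry the corrected table into later amlitelimab protocols.

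In this trial, produce one listing of randomized participants with positive HBc Ab or HCV Ab and an indeterminate HBV DNA or HCV RNA result at screening. Retest anyone found before the next dose, or before entry to the long-term safety study, subject to that study's own criteria, which are not among the documents.

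The cost is one line in each of two rows, matching words in E 13, one listing from existing data, and a repeat test for anyone found, possibly nobody. In later protocols the downside is an occasional repeat test or extra screen failure.
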